-Bolded Information Sheet(s)-

BOLDED_8089_CF_SUMMARY_11.13.23.pdf

-Miscellaneous Document(s)-

8089.MRIFindingsLetter.Uncertain Significance_2023.pdf

MRI Updates_Consent Form Guidance.pdf

TO_BE_APPROVED_8089_PHONE_SCREEN_SCRIPT_11.13.23.pdf

[name]_DMP_APPROVAL.pdf

8089_BOLDED_PSF_11.24.23.pdf

UNBOLDED_IE_CONFIRMATION_11.16.23.pdf

BOLDED_IE_CONFIRMATION_11.16.23.pdf

SRMP_Checklist 11.24.23.pdf

-Unbolded Consent Form(s)-

TO_BE_STAMPED_8089_CONSENT_11.13.23.pdf

TO_BE_STAMPED_8089_CONSENT_PROCEDURE_NOTE_11.13.23.pdf

-Unbolded Information Sheet(s)-

TO_BE_STAMPED_8089_CF_SUMMARY_11.13.23.pdf

-Unbolded Assent Form(s)-

NYSPI_8089_Unstamped_PCS_10 06 2023_English_Spanish.pdf

-HIPAA Form(s)-

To Be Stamped_8089_HIPAA_10 06 2023_English.pdf

## **Sample Size Calculation**

The main goal of the pilot study is to provide effect sizes of the outcomes to guide future larger trials. The target sample size of 50 participants (25 per arm) was chosen in accordance with the “stepped rules of thumb” for pilot trials proposed by Whitehead et al. (2016), which indicate that this sample size is mathematically optimal for a pilot study intended to inform the design of a future trial fully powered at 90% to detect a small standardized effect size (Cohen’s  $d=0.2$ ). In addition, this sample size yields a 95% confidence interval for the between-group difference with an approximate margin of error of 0.57 standard deviations, providing sufficient precision to estimate both the treatment effect and the population variance needed to plan a large trial.

## **Statistics**

Baseline variables will be summarized by treatment arms using means and standard deviations for continuous variables and counts and percentages for categorical variables. Analyses will include all participants according to the assigned treatment (intention to treat analyses).

Linear regression analyses will be conducted to evaluate treatment effects on change in imaging outcomes ( $^{18}\text{F}$ -Florbetapir PET SUVR, MRI-based hippocampal volume, MRI-based cortical thinning and plasma p-tau217) from baseline to 52 weeks, adjusting for baseline value of the imaging measure, age, sex and apolipoprotein E  $\epsilon 4$  positive status. Linear mixed effects models (LMM) will be used to assess the treatment effects on cognitive and functional outcomes (PACC, ADCS-ADL-PI, MMSE and CDR sum of boxes). Change score from baseline will be specified as the dependent variable, with treatment group, study time point (categorical), and their interaction included as predictors, adjusting for the baseline value of the outcome, age, sex, and apolipoprotein E  $\epsilon 4$  carrier status. Subject-specific random effects will be included to

account for within-subject correlation. Each model incorporates all available follow-up assessments at 12, 26, and 52 weeks.

Adverse events by treatment group will be summarized by frequencies of occurrence. Plasma acyclovir concentrations obtained at 52 weeks will be summarized using means and standard deviations. All statistical analyses will be conducted using R version 4.3.3. As this is a pilot study, statistical significance will be assessed using a two-sided alpha level of 0.05, with no adjustment for multiple comparisons.

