Hypothesis 2: Patients on valacyclovir will show smaller decline than patients on placebo on the PACC cognitive composite score (0 to 52 weeks).

Aim 3: Compare change in ADCS-ADL-PI on valacyclovir to placebo.

Hypothesis 3: Patients on valacyclovir will show smaller decline than patients on placebo on the ADCS-ADL-PI (function measure; 0 to 52 weeks).

Exploratory Hypotheses: We will explore apolipoprotein E e4 genotype as a moderator, and changes in global clinical status (CDR sum of boxes), viral antibodies and proteomic assays, AD signature of MRI regional and whole brain cortical thinning, and plasma total tau, p-tau epitopes and neurofilament light (NfL) protein markers for neurodegeneration.

Description of Subject Population

In this section, you are to describe each subject population of the study. The demographics of the population should reflect the gender and ethnic distribution of each population being studied. Enter each subject population's sample size, Gender, Racial, and Ethnic breakdown, and finally, describe each subject population.

We plan to enroll/randomize 56 participants. Of the 56 enrolled participants, we anticipate that 50 participants will "complete" the study, defined as completing Week 0 (Baseline) procedures and at least one additional follow-up visit, i.e., Week 12.

All 56 patients that we plan to enroll will need to meet criteria for diagnosis of amnesic MCI (eMCI and IMCI by ADNI criteria), HSV-seropositivity (HSV1 or HSV2, as specified in the Inclusion Criteria), and AD biomarker-positivity (positive 18F-Florbetapir Amyloid PET Scan or previous AD biomarker positive CSF – with low A β 42 and high tau/p-tau). Either gender will be included.

The majority of older adults have had the HSV infection during their lifetimes with persisting serum antibodies to HSV1 or HSV2. The prevalence of serum antibodies to HSV1 or HSV2 leads us to believe that the demographic breakdown of subjects with both MCI and HSV will not significantly differ from the breakdown of all subjects with a diagnosis of MCI.

Both English and Spanish speaking subjects will be enrolled.

The total recruitment numbers for NYSPI/Columbia are 50 completers required to accomplish study aims.

Sample Subject Population:

Subject Population	Number of completers required to accomplish study aims	Projected number of subjects who will be enrolled to obtain required number of completers	Age range of subject population

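### The SAP leaves the covariance of the repeated change scores open; a random-intercept fit, its natural reading, would understate the Week 52 standard error if change-score variance grows over follow-up

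*SAP*

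**What the plan says.** SAP, Statistics, sets out the mean model: "Change score from baseline will be specified as the dependent variable, with treatment group, study time point (categorical), and their interaction included as predictors", with adjustment for baseline value, age, sex and APOE ε4 status. The correlation model is one sentence: "Subject-specific random effects will be included to" "account for within-subject correlation". On visits: "Each model incorporates all available follow-up assessments at 12, 26, and 52 weeks". On testing: "statistical significance will be assessed using a two-sided alpha level of 0.05, with no adjustment for multiple comparisons".

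The protocol's paragraph on intent to treat and missing data adds only that longitudinal mixed models will be used under a missing-at-random assumption. It names no covariance structure.

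Protocol, Specific Aims and Hypotheses, frames both clinical hypotheses over the full year. Hypothesis 2 concerns decline on PACC from 0 to 52 weeks. Hypothesis 3 expects "smaller decline than patients on placebo on the ADCS-ADL-PI (function measure; 0 to 52 weeks"). The SAP does not say which contrast from the model answers them.

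SAP, Sample Size Calculation, says that the pilot is to supply effect sizes and the variance for sizing a later trial. It quotes a 95% margin of error of about 0.57 SD with 25 per arm.

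**The concern.** A random effect for each visit would put three random effects on three observations per patient, which cannot be separated from residual error. A random slope needs a numeric time variable, and the SAP mentions none. That leaves a random intercept with a single residual variance as the most likely fit. Its total variance is the same at every visit, so in effect it pools the three visit variances.

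Change from baseline in a progressive condition often spreads out with time because patients decline at different rates. The protocol points qualitatively the same way: it mixes early and late MCI, notes that a significant share of early-MCI patients decline, and allows some participants to run past 52 weeks. If the spread does grow, the pooled variance is too small for Week 52 and too large for Week 12. At stake are the Week 52 interval and p-value for Hypotheses 2 and 3, and the variance handed to the next trial.

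**Working it through.** **Inputs.** From the documents: 25 per arm, a margin of about 0.57 SD, two-sided 5%, visits at Weeks 12, 26 and 52, dropout 10%. Not in the documents, so assumed: how the SD of change varies by visit.

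**The plan's own figure.** Margin = critical value × √(2/25). With t on 48 df this is 0.569, which agrees with the stated 0.57 (a normal critical value gives 0.554). The sizes also agree: 50/0.90 = 55.6, so 56 randomized.

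**Formula.** With complete data and a full arm-by-visit mean model, the Week 52 contrast is the Week 52 difference in (adjusted) means. Its true SE is SD₅₂ × √(2/n). A random-intercept model with one residual variance reports √(mean of the three visit variances) × √(2/n). So

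SE ratio r = √(mean variance) / SD₅₂, and type I error ≈ 2 × [1 − Φ(1.96 r)].

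**A. Assumed SD ratios, Weeks 12:26:52.** Example for 0.8:0.9:1: (0.64 + 0.81 + 1)/3 = 0.817, and √0.817 = 0.904.

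| SD ratio | r | SE error | Type I | Margin shown (true 0.57) | Variance relative to true |
|---|---|---|---|---|---|
| 1:1:1 | 1.000 | none | 5.0% | 0.57 | 1.00 |
| 0.9:0.95:1 | 0.951 | 4.9% too small | 6.2% | 0.54 | 0.90 |
| 0.8:0.9:1 | 0.904 | 9.6% too small | 7.7% | 0.51 | 0.82 |
| 0.6:0.75:1 | 0.801 | 19.9% too small | 11.7% | 0.46 | 0.64 |
| 0.5:0.7:1 | 0.762 | 23.8% too small | 13.6% | 0.43 | 0.58 |
| 1.2:1.1:1 | 1.103 | 10.3% too large | 3.1% | 0.63 | 1.22 |

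**B. Assumed patient-specific slopes.** Take residual variance 1, baseline reliability 0.85 and annual slope SD s. Then Var(change at t, given baseline) = s²t² + 1 + 0.85, with t = 12/52, 26/52 and 1. The mean of t² is (0.053 + 0.25 + 1)/3 = 0.434.

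- s = 0.5: √[(1.85 + 0.109)/2.10] = 0.966, type I 5.8%.
- s = 1: √[(1.85 + 0.434)/2.85] = 0.895, type I 7.9%.
- s = 2: √[(1.85 + 1.738)/5.85] = 0.783, type I 12.5%.

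Two sets of simulations under model B with 56 patients and 12% dropout (1,500 and 500 replicates per setting) gave random-intercept type I errors of 5.0% and 6.6% at s = 0.5, 9.1% and 6.6% at s = 1, and 12.1% and 9.8% at s = 2. Fitting intercept plus slope gave mean SE/empirical SE of 1.00, 1.00 and 1.05, with type I error 5.8%, 5.8% and 3.2%.

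**C. Simulation with SD ratios.** 300 REML fits per scenario, 25 per arm, 10% dropout, four baseline covariates, adjacent-visit correlation 0.6. Each cell shows mean SE/empirical SE and type I error (t, 44 df).

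| SD ratio | Random intercept | Intercept + slope | Unstructured |
|---|---|---|---|
| 1:1:1 | 1.00, 6.3% | 1.01, 6.3% | 0.99, 6.0% |
| 0.8:0.9:1 | 0.85, 10.7% | 0.96, 6.7% | 0.95, 8.0% |
| 0.6:0.75:1 | 0.81, 10.7% | 1.01, 4.0% | 1.01, 4.0% |
| 1.2:1.1:1 | 1.04, 4.0% | 0.98, 6.3% | 0.95, 6.3% |

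Monte Carlo error is about 1.3 points on a 5% rate and about 4% on each empirical SE, so only the broad pattern should be read from this table. At 0.6:0.75:1 the random-intercept model put the Week 52 variance at 0.62 against a true 1.00. Required sample size is proportional to variance, so a trial sized on that figure would be about 38% too small.

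**The case against.** A reader might infer that the SAP forces a common variance. It does not. It speaks of random effects in the plural, does not limit them to an intercept, and does not declare the residuals homogeneous. A random intercept plus slope fits within its wording. Under the patient-specific-slope model in B that is the correct model, and in C it did about as well as the unstructured covariance. This stands.

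A reader might also infer that the Week 52 intervals will be too optimistic. The documents give no SD by visit for any of these outcomes, so they do not support that. Equal variances give no error and falling variances reverse it. At the mild end (s = 0.5) the effect is hard to tell from nominal, and the upper end needs an annual slope SD twice the residual SD or an equally steep SD ratio. This stands too.

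Three further points count against a strong reading. With complete data the Week 52 mean difference does not depend on the covariance choice, so the unstandardised effect estimate is safe. The Week 52 contrast can readily be inferred from the hypotheses even though it is not named. Holding the baseline coefficient constant across visits does not bias a randomized comparison.

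What remains is that the natural fit of an unspecified model is valid only if the variance is flat. The variance estimate, which the sample-size section presents as a product of the pilot, depends on this directly.

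**Conclusion.** The point holds conditionally. The SAP does not fix the covariance structure. If a random intercept with one residual variance is fitted, and if the variance of change rises by Week 52, the Week 52 SE would be about 3% to 24% too small and type I error about 6% to 14% over the scenarios assumed. The planning variance would be about 7% to 42% too small (1 − 0.966² and 1 − 0.762²). Rising variance is plausible here, but it is an assumption and not a figure from the documents. An intercept plus slope largely removes the problem for PACC, ADCS-ADL-PI and MMSE. It is not separately estimable for CDR sum of boxes, which the protocol's visit descriptions list at Weeks 26 and 52 but not at Week 12. This is a cheap improvement to the plan, not a demonstrated error in it.

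**What to change.** In SAP, Statistics:

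- Replace the random-effects sentence with an unstructured within-subject covariance across Weeks 12, 26 and 52, fitted by REML with Kenward-Roger or Satterthwaite degrees of freedom. State a fallback for non-convergence, for example visit-specific variances with a common correlation.
- Name the Week 52 arm difference in change as the estimate for Hypotheses 2 and 3, and report the Week 52 variance from the same model for planning.
- For CDR sum of boxes, use Weeks 26 and 52 only and amend the sentence that gives every model three follow-up visits.
- A baseline-by-visit term is optional.

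Cost: SAP wording, six covariance parameters (three variances and three covariances) instead of two with about 50 patients, and possibly a wider Week 52 interval. In return, the structure does not depend on which way the variance moves.
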